5.5 Secondary outcomes measures

• The number of participants with adverse events within 30 days of surgery using the Medical Dictionary for Regulatory Activities.

- Antibiotic resistance to clinically relevant antibiotics will be evaluated in isolates from participants' wounds at diagnosis of SSI and after 7 days if no response to treatment. This will be assessed by a central microbiology laboratory (Public Health Wales).
- Health-related QoL measured by EQ-5D-5L questionnaires at baseline, 30 days and 3 months.
- Time to return to normal activity/work at 30 days and 3 months.
- Resource use (related to wound complications including SSI) and cost of hospital visits/stays at 30 days and 3 months.
- Qualitative process evaluation assessing implementation and acceptability of oral antibiotics including facilitators and barriers.
- Feasibility of 'Selfi-wound' photos as measured by the number of participants who were able to successfully take and transmit an image of their wound images via the online system.
- Validation of WHQ remote use for SSI assessment via SWAT.

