All participants will receive the standard wound care advice that they would normally receive as part of routine NHS standard of care with possible signs and symptoms of SSI explained to them. Participants will also be given clear written and pictorial material (designed in collaboration with our Patient Partners), including what to look for to identify a wound infection. Participants will be reassured that prompt treatment will be available for any participants with SSI. All participants will be given contact details (including out-of-hours where applicable) of their local recruiting centre and will be advised to contact their local recruiting centre if they have any concerns about wound infection or side effects from the antibiotic tablets to arrange a face-to-face review. Financial assistance will be provided towards participant transport costs for the face-to-face review (if required) to support people on low incomes to participate in the trial, in line with recommendations from the NIHR INCLUDE Socioeconomic Disadvantage Framework (55).

We recognise that some participants with symptoms of wound infection may seek medical advice locally from another health care professional e.g., GP, out-of-hours GP, Emergency Department however participants will be given emergency contact details of their local recruiting site and will be asked to contact them if an SSI is suspected. Suspected SSIs will be assessed at local recruiting site and if an SSI is confirmed, participants will be requested to provide a wound swab, and again 7 days later if infection has not responded to treatment, as per CDC criteria (16).

IRAS: 1009425

Follow-up procedures

Participants will be provided with a patient diary to capture their subjective journey through the trial, and record any symptoms of SSI and notes on their general health, to aid in completion of follow-up assessments by the research team.

All participants will be telephoned by the local research team around days 5-10, days 15-20 and at day 30 (+/-7 days) following surgery to ask about any concerns about wound infection or side effects.

Participants will be encouraged to identify a nominated support person (e.g. a family member) to assist them with trial-related activities, such as wound photos and completing questionnaires, which will support the inclusion of digitally excluded populations and participants with cognitive impairment/ impaired capacity.

SSI diagnosis

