11.2 Follow-up

Day 30 (+/- 7 days) and 3 month (+/- 7 days) follow ups will be completed by telephone/email/post by the research nurses.

30-day follow-up:

- Adverse events
- New antibiotics
- SSI telephone assessment with face-to-face wound review if patient/clinician concern
- Wound swabs if SSI diagnosed
- Participant QoL EQ-5D-5L Questionnaire and Bluebelle WHQ questionnaire.

IRAS: 1009425

- Time to return to normal work/ activity
- Resource use (related to wound complications including SSI including report of hospital visits/stays)
- Qualitative interviews (optional n=40)

3-month follow-up:

- Participant QoL EQ-5D-5L Questionnaire
- Time to return to normal work/ activity
- Resource use (related to wound complications including SSI including report of hospital visits/stays)

Around three attempts will be made to contact the participant at each follow-up by telephone. If it is not possible to contact participants, the participant's support person (if nominated) may be contacted as an alternative. If all contact attempts are unsuccessful, a questionnaire booklet may be posted to the participants for them to complete and return.

The follow-up period will end 3 months (+/- 7 days) after the last recruited participant has been randomised and initiates medication (at completion of their 3-month follow-up assessment).

GYMRU Caerdydd a'r Fro
NHS
WALES University Health Board Bwrdd Iechyd Prifysgol Caerdydd a'r Fro

	Assessment	Source Data	Data type/Measure	Screening & Baseline	Day 5-10	Day 15-20	Day 30 (+ 7/7)	3 months (+ 7/7)	Responsible for Data Collection	Justification
1	Eligibility Assessment	Screening log, CRF, documented in medical notes	Inclusion /Exclusion criteria	X					Qualified medical professional with delegated responsibilities	Eligibility
2	Informed consent	Consent form, documented in medical notes	Informed consent	х					Qualified medical professional with delegated responsibilities and site research team who are appropriately qualified, experienced and delegated by the PI	Consent
3	Demographics	CRF	- Age - Sex - Gender - Ethnicity	Х					Site research team	Baseline
4	Contact details	CRF	- Contact details (inc. Postcode) - Alternative Contact details - GP Contact details - NHS number	Х					Site research team	Trial Management
5	Medical history	CRF, documented in medical notes	Co-occurring conditions	Х					Participant Reported/ Site research team	Baseline

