14.5 Reporting procedures

14.5.1 Participating Site Responsibilities

The PI (or delegated medically qualified doctor from the trial team) should sign and date the SAE CRF to acknowledge that he/she has performed the seriousness and causality assessments. Investigators should also report SAEs to their own health boards or trust in accordance with local practice.

A completed SAE form for all events requiring immediate reporting should be submitted via fax or email to the CTR within 24 hours of knowledge of the event. A separate form must be used to report each event, irrespective of whether or not the events had the same date of onset.

The participant will be identified only by trial number, month, and year of birth and initials. The participant's name (or any other personal identifiers) should not be used on any correspondence.

It is also required that sites respond to and clarify any queries raised on any reported SAEs and report any additional information as and when it becomes available through to the resolution of the event. Additionally, CTR/ pharmaceutical companies may request additional information relating to any SAEs/ SARs and the site should provide as much information as is available to them in order to resolve these queries.

Serious Adverse Event (SAE) email address:

[contact]

SAE [contact]

SAEs should be reported from time of randomisation, and up to, and including 30 days after the participant receives their dose of the IMP. SARs (such as long-term side effects of trial treatment under investigation) should continue to be reported until the end of follow up as defined in the protocol.

SAEs should be graded using the NCI Common Terminology Criteria for Adverse Events (CTCAE) Version 5.0.

IRAS: 1009425

An SAE form should contain at least the minimum information:

• Full participant trial number.

- An Adverse Event / Adverse Reaction.
- Trial intervention.
- A completed assessment of the seriousness, and causality as performed by the PI (or another appropriately medically qualified doctor registered on the delegation log).

If any of these details are missing, the site will be contacted, and the information must be provided by the site to the CTR within 24 hours.

Except SSIs, no other AEs should be reported on the CRF as Flucloxacillin is a marketed product with a significant amount of safety data available.

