16.2 Cost effectiveness analysis

With the potential for SSI's increasing use of health care resources (59) alongside the impact on quality of life (12) whilst considering the economic impact of antibiotic stewardship programmes (60), a health economic evaluation as part of the EXCISE trial will be conducted to assess the cost- effectiveness of a single pre operative dose of oral flucloxacillin and standard care compared to no antibiotic and standard care for ulcerated skin cancers. The evaluation will be designed, conducted and reported following best-practice guidelines (61), with a Health Economic Analysis Plan (HEAP) produced as part of a comprehensive SAP as detailed earlier. A UK NHS/ Personal Social Services Perspective will be taken for the base-case (primary) analysis. Discussions with the EXCISE research team and patient representatives during the development of the EXCISE grant submission highlighted the impact of managing SSIs to the patient and society, thus an additional (restricted) societal perspective to collect additional costs (e.g., out of pocket expenses) alongside time away from usual activities (e.g., loss of workdays) will be included as supplementary analysis. Economic outcomes will be collected as part of the EXCISE data collection schedule, described earlier.

Resource use data associated with the primary surgical procedure (e.g., length of visit/stay) and antibiotic use will be gathered via the trial case report forms. Subsequent health and care resource use data related to wound complications, including SSI, will be collected, alongside key personal costs and lost workdays. The resource use data collection measure/schedule will be developed in collaboration with the EXCISE research team and patient representatives, drawing upon good practice to balance the requirement for comprehensive information against the burden (both participant and researcher) of completion (62,63). The internal pilot phase will assess the collection of economic outcome measures and inform the first iteration of the HEAP. Published UK unit costs will be used to value resource use in £ sterling to the most relevant price year available at time of final analysis. Total and per participant costs will be presented based on the available case dataset to provide a comprehensive summary of the resource use and costs associated with the intervention and comparator groups over the trial period.

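### Follow-up resource use is limited to wound complications, so contacts for suspected side effects of the trial medication go uncosted and the cost-effectiveness result can be biased towards flucloxacillin

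*Protocol*

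**What the plan says.** Protocol 16.2 sets the costing viewpoint: "A UK NHS/ Personal Social Services Perspective will be taken for the base-case (primary) analysis". It names two streams of NHS resource data. The first covers the operation and antibiotics: "Resource use data associated with the primary surgical procedure (e.g., length of visit/stay) and antibiotic use will be gathered via the trial case report forms". The second covers later care: "Subsequent health and care resource use data related to wound complications, including SSI, will be collected". Personal costs and lost workdays are added for the supplementary societal analysis.

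The secondary outcome in 5.5 reads "Resource use (related to wound complications including SSI) and cost of hospital visits/stays at 30 days and 3 months", and the synopsis carries the same outcome. The 30-day and 3-month lists in 11.2 read "Resource use (related to wound complications including SSI including report of hospital visits/stays". Table 2, row 16, says only that health economic data and resource use are collected.

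Section 11 (Post Surgical Care Procedures) tells participants to contact their recruiting centre "if they have any concerns about wound infection or side effects from the antibiotic tablets to arrange a face-to-face review".

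On safety data, 14.5.1 says "Except SSIs, no other AEs should be reported on the CRF as Flucloxacillin is a marketed product". It sets the serious-event window as follows: "SAEs should be reported from time of randomisation, and up to, and including 30 days after the participant receives their dose of the IMP". Serious adverse reactions are reported to the end of follow-up.

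**The concern.** An economic evaluation of a prophylactic drug should cost the care that the drug may prevent and the care that it may cause. Here the first is collected and the second is not. The protocol itself gives unwanted side effects as a reason to avoid unnecessary antibiotics (3.3 and 4.1), and it sets up a route by which participants with such effects use NHS time. A review for suspected infection falls within the costed scope. A review arranged through the same telephone number for a suspected reaction to the capsules does not.

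The incremental cost per QALY, the net monetary benefit and the cost per SSI prevented all use this cost difference. The exploratory longer-term model, which relies on trial evidence for its parameters, could inherit the gap.

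**Working it through.** The protocol gives no cost figure to reproduce, so the check is first one of scope and then one of possible size.

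**Where could a side-effect contact be recorded?**

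| Source | What it captures | Does it cost a side-effect contact? |
|---|---|---|
| 16.2, 5.5 and 11.2 resource use | Care related to wound complications including SSI | No, except possibly hospital visits under 5.5 (see below) |
| 16.2, CRF items | Primary procedure and antibiotic use | No |
| 10.8, concomitant drugs | Antibiotics, antithrombotics, immunosuppressants | No; drugs for a rash or gut upset need not appear |
| 14.5.1, safety data | SAEs to 30 days after the dose, SARs to end of follow-up | Admissions are recorded, with no stated link to costing |
| 9.1 and 11, diary and calls | Concerns about side effects | No; nothing says the resulting care use is recorded |

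GP visits, site reviews and other outpatient contacts for suspected side effects therefore have no stated source.

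**Hospital visits.** In 5.5 the bracket closes before the cost of hospital visits and stays, so those costs can be read as unrestricted. In 11.2 they sit inside the wound-complication bracket. The two cannot both define the outcome. Neither reading brings in GP contacts for side effects.

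**Direction.** Contacts that are equally frequent in both arms cancel. Let s be the excess proportion of flucloxacillin participants with a side-effect contact and c the cost per contact. The omitted incremental cost per participant is s × c, which understates the cost of flucloxacillin if s > 0.

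**Size.** The protocol gives neither s nor c. Assumed ranges are s = 1% to 10% and c = £50 to £300.

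- Lowest: 0.01 × £50 = £0.50 per participant.
- Highest: 0.10 × £300 = £30 per participant.
- At c = £150: 0.01 × 150 = £1.50, up to 0.10 × 150 = £15.

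To scale the £150 case, take the planned 15-point SSI reduction from 15.3:

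| Cost per SSI | Saving per participant | £1.50 to £15 as a share |
|---|---|---|
| £500 (assumed) | 0.15 × 500 = £75 | 2% to 20% |
| £1,000 (assumed) | 0.15 × 1,000 = £150 | 1% to 10% |
| £10,000 (Section 4 gives over £10,000, from other surgical specialties) | 0.15 × 10,000 = £1,500 | 0.1% to 1% |

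At £20,000 per QALY, £1.50 to £15 corresponds to 1.50/20,000 = 0.000075 up to 15/20,000 = 0.00075 QALY.

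**Possible offset.** Suppose side effects of antibiotics given to treat an SSI are also left out, every SSI is treated with antibiotics, and the unit cost is the same. Let t be the proportion of treated participants with a side-effect contact. The placebo arm then has an omitted excess of 0.15 × t × c. The net omission, (s − 0.15t) × c, changes sign when t/s exceeds 1/0.15 = 6.7. For s = 1% that means t above 6.7%; for s = 10% it means t above 67%.

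**The case against.** A reader might infer that the result is biased by construction, with its sign fixed in favour of flucloxacillin. The documents do not support that. A bias needs more care-seeking after one active dose than after placebo, and no section shows such an excess. Section 4.1 describes side-effect rates as low, and under blinding placebo participants will report side effects too. Care for side effects of SSI treatment would fall mainly on the arm with more infections. If that care is also left out, it offsets the omission and could outweigh it when the single-dose excess is small. This part of the objection stands.

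A reader might also infer that admissions are lost and that harms vanish from the evaluation. Hospitalisation makes an event an SAE (14.1), reported in both arms to 30 days after the dose, so the costly tail is recorded even though no section routes it to costing. Adverse events and resistance remain secondary outcomes in 5.5, and EQ-5D-5L feeds the QALYs, although measurement at baseline, 30 days and 3 months will largely miss brief early effects. What is missing is one cost component, mostly low-cost outpatient contacts.

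Finally, 16.2 says the resource-use measure is still to be developed, balances completeness against burden, and leaves detail to a health economic analysis plan. This answers less. The scope is set in the protocol, and no analysis plan can cost contacts that were never recorded. A sensitivity analysis or a literature-based model could add assumed side-effect costs, but not the trial's own.

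**Conclusion.** The concern holds in a limited form. As written, the protocol leaves outpatient, GP and site contacts for suspected side effects uncosted, and it does not send admissions reported as SAEs to the costing. This sits badly with the NHS/PSS base case and with the promise in 16.2 of a comprehensive cost summary for both arms.

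The incremental cost is understated, and the result can be biased towards flucloxacillin, only if a single dose causes more such care than placebo and this is not offset by side effects of SSI treatment. The illustrative £0.50 to £30 per participant rests wholly on assumed inputs. At the planned effect the omission is unlikely to change the conclusion; it would carry more weight if the SSI difference proved small. The case for acting is that the omission is avoidable, possibly one-sided and cheap to close before the form is built.

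**What to change.** In 5.5 (and the matching synopsis entry), 11.2, Table 2 row 16 and 16.2, widen the resource-use question in both arms. It should cover care related to wound complications including SSI, or to suspected side effects of the trial medication or of antibiotics given for SSI. Record the reason for each contact, including the side-effect reviews that Section 11 invites. Include these costs in the base case, together with admissions reported as SAEs and judged to be suspected side effects, counting each admission once.

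Reconcile 5.5 with 11.2 so that it is clear whether hospital visits and stays are restricted to wound complications.

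The cost is one added reason category on a form still to be developed, and slightly longer questionnaires at two existing contacts (30 days and 3 months). Clinical management and sample size are unaffected.

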16.3 Qualitative Study and Process Evaluation

It is important to encompass assessment of the fidelity of possible influences on treatment outcomes in the design and implementation of surgical randomised controlled trials (70).

Our aim is to understand the factors affecting trial compliance, wound management and reporting SSI. We will ensure representation across sites, patient demographic characteristics. We will also explore the participants' wound burden through the participants perspective.

We will conduct semi-structured interviews with trial participants (n=40) sampled purposively, to ensure appropriate diversity, and include those reporting good and poor outcomes from each trial arm, with interviews conducted following the 30-day wound assessment. Potential patient interview participants will be given a PIS about the qualitative interview study.

For patients willing to take part in the qualitative aspects of the EXCISE trial, they will be asked by the local site PI or Research Nurse to complete a consent to contact form. For those that opt to consent to participate in an interview, the QR will be notified and participant details reviewed for sampling (site, age, gender, trial arm, surgical site). Those then sampled for interview will be contacted by the QR and sent the PIS for interviews, along with a consent form, elicitation guidance document, diary booklet, timeline example and stamped addressed envelope. Once potential participants have had time to consider the study information the QR will contact them to discuss consent and arrange a suitable time for an interview.

Trial participants approached for interview will be invited to complete a diary and visual timeline elicitation activity to capture their subjective journey through the trial. The diary and timeline will be used in the conduct of in-depth semi structured interviews with trial participants. The inclusion of a diary and visual timeline will aid and enhance the communication between the researcher and participant and provides data in an alternate mode of expression type that can help researchers understand complexity and open up discussions that may have remained unspoken and unexplained. The representation of participant's experience through diaries and timelines will promote narrative accounting and allow the participant and researcher to focus on eliciting a shared understanding of the acceptability of treatment received including views on antibiotics, barriers and facilitators and the wound burden.

We will include a sample of participants (n=8) deemed ineligible or declined to take part, to explore views on antibiotic prescribing and use, and barriers to participation. These participant interviews will be undertaken post-screening.

In-depth semi-structured interviews will be undertaken with healthcare professionals (n=20) purposively sampled to include pharmacists (across 10-15 sites). Interviews will explore issues of implementation, equipoise, and the experience and acceptability of prescribing in practice.

All interviews will be undertaken remotely via telephone or videoconference, audio recorded, transcribed and anonymised. Patients will be invited to include a relative or friend in the interview if they wish.

We will develop an a-priori framework and framework analysis of qualitative data will be undertaken. This systematic five stage method accommodates multiple data sources such as diaries, timelines and interviews and allows for the comparison of themes across treatment centre, trial arm, participant outcome and participant/interviewee category.

We will undertake a rapid evaluation with a sub-sample of interviews with trial participants (n=8) and HCPs (n=4) during the pilot phase to explore acceptability of the study design and outcome measures. Data will be analysed thematically and we will pay attention to eligibility and recruitment experiences and challenges, facilitators and barriers affecting recruitment, including patient preferences and any issues with clinical equipoise and implementation. Findings from a rapid evaluation of early interviews will be fed back to the TMG during the pilot phase with recommended actions.

17 Data Management

The detailed data management processes used in the EXCISE trial are documented in the EXCISE Data Management Plan.

Source Data is defined as "All information in original records and certified copies of original records of clinical findings, observations or other activities in a clinical trial necessary for the reconstruction and evaluation of the trial. Source data are contained in source documents.". There is only one set of source data at any time for any data element, as defined in the site source data agreement. The source data for the EXCISE trial will be from a variety of sources as described in Table 2.

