Once potential interview participants have had time to consider the study information, potential interview participants will be asked by a delegated member of the research team tick the qualitative statement on the informed consent form or complete a consent to contact form as appropriate for trial participants or HCPs. For those that opt to consent to participate in an interview, the Qualitative researcher (QR) will be notified and participant details reviewed for sampling (site, age, gender, trial arm, surgical site). Those then sampled for interview will be contacted by the QR and sent the PIS for interviews, along with a consent form, elicitation

guidance document, diary booklet, timeline example and stamped addressed envelope. Once potential participants have had time to consider the study information the QR will contact them to discuss consent and arrange a suitable time for an interview.

Patients who are eligible for trial participation but decline to participate may opt to consent to participate in qualitative interviews. Health professionals involved in the trial may consent to participate in qualitative interviews.

After the participant has entered the trial, the investigator must remain free to give alternative treatment to that specified in the protocol, at any stage, if they feel it to be in the best interest of the participant. However, the reason for doing so should be recorded and the participant will remain within the trial for the purpose of follow up and data analysis according to the treatment option to which they were allocated. Similarly, the participant must remain free to withdraw at any time from the protocol treatment without giving reasons and without prejudicing their further treatment (see Section 13.1 or further details on Withdrawal).

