15.2 Blinding

Participants, clinicians and outcome assessors will be blinded to the randomised allocation. Further details will be included in the trial Unblinding plan.

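### Trial arm is used to pick interviewees while the trial is still blinded, and the protocol does not keep it from the qualitative researcher who interviews them

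*Protocol*

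**What the plan says.** Section 9.4 (Informed consent) says that for participants who opt in to interview "the Qualitative researcher (QR) will be notified and participant details reviewed for sampling (site, age, gender, trial arm, surgical site"). Section 16.3 repeats the rule, again with the researcher notified and "participant details reviewed for sampling (site, age, gender, trial arm, surgical site"). In both places the next step is that the qualitative researcher contacts the people selected and arranges the interview.

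Section 16.3 sets the sampling target: 40 trial participants, chosen purposively to "include those reporting good and poor outcomes from each trial arm, with interviews conducted following the 30-day wound assessment". It describes a framework analysis that "allows for the comparison of themes across treatment centre, trial arm, participant outcome and participant/interviewee category". It also plans a rapid evaluation of 8 participant and 4 health-professional interviews during the pilot, and states: "Findings from a rapid evaluation of early interviews will be fed back to the TMG during the pilot phase".

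The synopsis calls the trial double-blind. Section 15.2 states: "Participants, clinicians and outcome assessors will be blinded to the randomised allocation". It leaves further detail to an Unblinding plan, which is not among the documents at hand.

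**The concern.** Choosing interviewees by outcome within arm means that somebody must look up allocation, together with outcome, for identified participants while the trial is running. The protocol does not say who that is. It places the review in the same clause as notifying the qualitative researcher, who then talks to the participant.

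Three things are exposed if the interviewer knows the arm:

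- **The interview data.** Section 5.5 lists the qualitative process evaluation as a secondary outcome. Section 16.3 says the interviews cover acceptability of the treatment received and views on antibiotics. Knowing the arm can steer the questions and colour the coding.
- **The 3-month outcomes.** EQ-5D-5L, return to normal activity and resource use are still to come for the same participants. The first two are wholly participant-reported, and EQ-5D-5L feeds the cost per QALY at 3 months (section 16.2). A cue about allocation during the interview could affect those answers.
- **Contact with blinded staff.** The qualitative study also interviews 20 health professionals and reports to the Trial Management Group (TMG). Section 6 says the TMG includes Principal Investigators of five lead recruiting sites.

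**Working it through.** The plan gives no figure on this point and nothing numerical decides it. The check is a comparison of sections, a timeline and a sense of scale.

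**1. Is arm needed before the interview?** Yes. Both section 9.4 and section 16.3 list it among the sampling details, so a single slip of drafting is unlikely. The target of good and poor outcomes from each arm cannot be met on purpose without it.

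**2. Who sees it?** The review is written in the passive and no reviewer is named. The qualitative researcher is the only person mentioned in the clause and makes the next contact, so that person is the natural reader. The text would also fit selection by someone else.

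**3. Which outcomes are still open?** Inputs: interviews follow the 30-day assessment (16.3); the last follow-up is at 3 months (11.2).
- Taking 3 months as about 90 days: 90 − 30 = 60 days, or about two months, between the earliest interview and the 3-month reports.
- For an interviewee the day-30 SSI assessment comes first, so that person's primary outcome is not exposed by this route.
- Still open are EQ-5D-5L and return to activity (participant-reported in Table 2) and resource use (participant or site team in Table 2).

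**4. What is the trial doing at the time of the pilot feedback?** Section 27 puts the pilot in months 10–15 and the rest of recruitment in months 16–24, so up to 24 − 15 = 9 months of recruitment remain. Section 16.3 describes the rapid evaluation in terms of acceptability, eligibility, recruitment, barriers, equipoise and implementation. It is not described as by arm.

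**5. Scale.**
- Interviews planned: 40 / 380 = 10.5% of participants.
- Pilot interviews: 8 / 57 = 14.0% of those expected by the end of the pilot (section 9.1), or 8 / 380 = 2.1% of the whole trial.
- Details are reviewed for everyone who opts in, not only for those interviewed. That number is not given, so 10.5% counts planned interviews. It measures neither the arms looked up nor any bias.

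**6. Does the protocol state a safeguard for this route?** None was found. No section gives the selection to an independent person, codes the arm, delays its release or bars the interviewer from passing it on. Elsewhere allocation is protected: section 7 requires sites to avoid accidental unblinding through electronic records, and section 14.7 assigns SUSAR unblinding to the safety group of the Centre for Trials Research (CTR).

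**7. Could someone else draw the sample?** The CTR supplies the randomisation list (10.2), has a safety group that unblinds (14.7), and the trial has an interim analysis that compares arms (15.3, 16.1.1). Allocation is therefore already held or used by people other than the interviewer.

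**The case against.** The strongest reply is that no stated blinding rule is broken. Section 15.2 names participants, clinicians and outcome assessors. The qualitative researcher is not on that list, and section 11 ties outcome assessment to blinded health professionals. Treating the interviewer as an outcome assessor because the process evaluation is a secondary outcome stretches the term. The access rules may also sit in the Unblinding plan or the Data Management Plan. This stands: nothing here shows a breach, and safeguards may exist elsewhere.

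A reader might infer that the interviewer is definitely told each participant's arm, or that allocation will reach participants and the TMG before outcomes are complete. The documents do not support either. The wording is passive, no section orders or describes disclosure to participants, and the pilot feedback is not by arm. The 3-month data are reported by participants or collected by site staff, not by the qualitative researcher. Bias would need the interviewer to know the arm, to give it away, and the participant to answer differently as a result.

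The objection does not remove the rule itself. The protocol names arm as a detail reviewed for sampling during the blinded period, twice, and puts no limit on who sees it.

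**Conclusion.** The point holds as an avoidable risk created by a stated rule, not as a demonstrated breach or bias. It concerns the interview findings and the later self-reported outcomes of up to 40 interviewees (10.5% of 380). It does not touch those participants' day-30 SSI result. Any effect on the TMG or on other participants is only a possibility.

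The conclusion assumes that the qualitative researcher is the person who reviews the details, which is the natural reading but is not stated. It also assumes that the unseen Unblinding plan does not already prevent this. If it does, sections 9.4 and 16.3 still need wording that agrees with it. The change is worth making because the protocol's aims, sampling across arms and comparing themes by arm, can both be kept without the interviewer knowing allocation.

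**What to change.** - In sections 9.4 and 16.3, remove trial arm from the details available to the qualitative researcher.
- State that a person at the CTR who already holds allocation, and is outside trial delivery and the interviews, selects by arm and outcome. That person gives the researcher the selected participants' IDs and contact details, with neither arm nor any grouping by outcome within arm.
- Link arm to the transcripts for the by-arm comparison of themes only after database lock.
- Align the Unblinding plan with this wording.

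**Cost:** a wording change to the protocol and the Unblinding plan, a little more work for the selector, and a by-arm qualitative comparison that waits until lock. The protocol does not name a suitable selector, so the CTR must confirm that one is available.
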